Rapid reduction of sNVP with mirtazapine treatment has been reported in case series of pregnant persons^{17,18} who have not responded to other medications. These cases include mothers who requested terminations of desired pregnancies due to inability to tolerate sNVP. Reproductive outcomes for mirtazapine do not indicate an elevated risk for birth defects, although the number studied is relatively small (≈500). Medications commonly used to treat sNVP are first-line drugs; however, a substantial number of pregnant persons do not respond adequately and novel therapeutics are urgently needed.

Mirtazapine is a compelling candidate to expand therapeutic options for sNVP. This exploratory/developmental phase 2 project is designed to determine whether a Phase 3 randomized controlled trial (RCT) is warranted by establishing the acceptability, tolerability, dosing and safety of mirtazapine for sNVP. Mirtazapine is not approved by the FDA for treatment of nausea and vomiting of pregnancy (NVP); therefore, in this clinical trial, mirtazapine is an investigational product.

We will conduct a 3-week open trial of 25 pregnant persons who have not responded to at least two antiemetic drugs. We hypothesize that mirtazapine will exhibit satisfactory acceptability, tolerability and safety in pregnant persons with sNVP. After the initial trial, a continuation period or a mirtazapine tapering regimen with monitoring will be offered. The aims of the trial are:

1. Determine the acceptability of mirtazapine for sNVP that does not respond to two standard drugs.

2. Define the tolerability and safety of an escalating 3-week mirtazapine dose regimen.

3. Assess the duration of treatment required following the initial 3-week trial and the adequacy of a tapering regimen for persons who discontinue mirtazapine.

4. Determine pregnancy and neonatal outcomes for all enrolled persons. We will collect data on delivery outcomes only with the peripartum events scale

5. Explore the relationship of study drug dose and plasma concentration with side effects and pharmacogenetics by obtaining weekly plasma.

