Both compliance with treatment and vomiting within an hour of the dose will be recorded in REDCap (along with the daily PUQE score) to evaluate these factors in the interpretation of

plasma concentrations. Mirtazapine treatment will continue unless the participant withdraws consent, experiences a limiting side effect or an obstetrician decides that the health risk to the patient compels discontinuation. At the end of the 3-week trial, subjects will be asked whether they prefer to continue mirtazapine, which will also serve as a measure of treatment satisfaction. Pregnant persons who choose to stop treatment will be given a taper regimen in reverse order of the dose escalation required for the 3-week trial. For example, if a patient is taking 45 mg at the end of week 3, she will begin a taper (by week) of 30 to 15 to 7.5 to 0 mg. If she relapses or has discontinuation symptoms, the previous effective dose will be given. She may attempt to taper again with the same approach. Participants who continue to be treated with mirtazapine in the continuation phase will be followed monthly throughout pregnancy unless they withdraw consent.

Maintenance Drug Treatment (Figure 4). For pregnant persons who choose to continue treatment, mirtazapine will be prescribed at the dose achieved at the end of the 3-week trial. The duration of treatment will be decided by the patient with a study obstetrician based upon her response and comfort with drug discontinuation. These data will be novel since no information on the duration of treatment with mirtazapine in persons with sNVP is available. For persons treated until delivery, maternal and cord blood will be obtained for plasma mirtazapine concentration measurement to evaluate placental transfer. If postpartum mirtazapine treatment is desired, it will be coordinated with our Collaborative Care Perinatal Services (COMPASS - the integrated mental health program in the Obstetrics department), or in the Asher Center in the Department of Psychiatry, which [name] directs.

Figure 4: Data Collection: Continuation Treatment					
Maintenance (every 4 weeks)	Delivery				
Wt, Ht, BP PUQE GH Plasma PHQ-9 GAD-7 C-SSRS ASE SS Medication Log	PES Maternal and umbilical cord blood				
Log PUQE=Pregnancy Unique Quality of Emesis; PHQ-9=Patient Health Questionnaire; GAD-7 =Generalized Anxiety Disorder; C-SSRS=Columbia-Suicide Severity Rating Scale; ASE=Asberg Side Effects; SS=Screen for Serotonin Syndrome. PES, Peripartum Events Scale.					

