PROMIS Global Health⁶³: The PROMIS Global Health item scale assesses overall health. The global health items include ratings of the five primary PROMIS domains (physical function, fatigue, pain, emotional distress, social health) as well as perceptions of general health that cut across domains. Global items allow respondents to weigh together different aspects of health to arrive at a "bottom-line" indicator of their health. Similar global health items have been found predictive of future health care utilization and mortality. The PROMIS Global Health items include the most widely used single self-rated health item ("In general, would you say your health is . . ."). Previous research has shown that this item taps physical and mental health about equally but reflects physical health more than mental health among respondents at lower income levels. PROMIS Global Health items include specific ratings of physical health and mental health, as well as a rating of overall quality of life. The remaining items provide global ratings of physical function, fatigue, pain, emotional distress, and social health. The PROMIS Global Health items can be administered as individual items or combined to produce separate physical and mental health summary scores.

Columbia-Suicide Severity Rating Scale (C-SSRS)⁷⁷: The Columbia-Suicide Severity Rating Scale (C-SSRS) is a questionnaire used for suicide assessment that was developed with NIMH support. The scale is evidence-supported and is part of a national and international public health initiative involving the assessment of suicidality. Suicidal ideation will be assessed at baseline, during, and 28 days after treatment cessation if there were any abnormalities during the trial.

DATA AND SPECIMEN BANKING

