12/23	19-24	Plasma conc and DNA Analyses; Summary Variables and Statistical Analyses; Manuscript finalization and submission; Final IRB, DSMB and IRB reviews; Draft R01 Phase 3 submission if warranted.	25= target			

INCLUSION AND EXCLUSION CRITERIA

Figure 6: Inclusion and Exclusion Criteria						
Inclusion Criterion	Rationale					
Ages 18-49 years	Age of adult childbearing persons					
Singleton pregnancy	Appropriate for initial Phase 2 trial					
Inpatient or outpatient status	Target is pregnant persons with refractory sNVP					
Care within Prentice Women's Hospital maternity practices	Retain subjects through pregnancy; coordinate with obstetrical care					
English speaking	Measures in English, staff are English speaking					
Obstetrician's evaluation and diagnosis of sNVP or HG	Differentiate from medical disorders (i.e. pancreatitis, appendicitis)					
Tolerance of oral disintegrating tablet at bedtime	Preparation is appropriate for persons experiencing emesis					
PUQE score of 10-15; moderate/high or severe	Pharmacotherapy is appropriate for this level of severity					
Refractory sNVP	Inadequate response to two commonly used drugs					
Anti-emetics may be continued as in real-world practice	Focus is mirtazapine for sNVP non-responsive to other medications					
Exclusion Criterion	Rationale					
Allergic or adverse reaction to mirtazapine	Inappropriate treatment					
Patient has bipolar disorder without anti-manic drug treatment	Risk for hypomania/mania induction					
Subjects with active depression, or history of or current active suicidal ideation or attempt	Mitigate risk for suicidality					

VULNERABLE POPULATIONS

The disease studied, sNVP, is specific to pregnant individuals. Case series studies of pregnant persons with sNVP or HG and who were treated with mirtazapine are reviewed in the Research Strategy section. Mirtazapine is FDA-indicated for the treatment of depression, and data on reproductive outcomes are available from treatment of this group of people. Additional information on pregnancy outcomes and neonates will be collected from the delivery record.

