Authorized research personnel will work with clinicians from the Northwestern Obstetrics and Gynecology services and the Obstetrical Triage program to identify potentially eligible individuals and approach them about their interest in participating. We have defined several eligibility criteria to allow participants to be screened by our study team. Subject burden can be reduced and study efficiency improved by asking only those subjects likely to be eligible to undergo a full baseline assessment. The screen includes: 1) age 2) gestational age of the fetus, 3) confirmation of plan to receive care and deliver at Prentice Women's Hospital (PWH), 4)

PUQE score of 10-15, 5) has been treated with at least two anti-emetic/antinauseant drugs with inadequate response; and 8) English speaking.

The inclusion/exclusion criteria will be reviewed in the patient's chart and documented on the screening log. If a patient meets all the inclusion criteria for enrollment, does not have any of the exclusion criteria, she will be approached about the study by authorized personnel. Her primary obstetrician will be contacted to review the patient's participation.

Brochures will be available to provide potential subjects with additional information. We will also post information about this study on our Asher Center and Northwestern Medicine websites, as well as post on the NCT site.

COMPENSATION FOR PARTICIPATION IN RESEARCH ACTIVITIES

Participants will be compensated with \$35 for each week of the three-week trial. If a participant wishes to participate in the continuation period or a mirtazapine tapering regimen, they will continue for 5 additional weeks and compensated with \$35 each week.

If a participant enters into the study early in pregnancy (gestational age of 5 weeks), they will have monthly visits after the 8 weeks is completed, for a maximum total of 10 visits.

Compensation will be provided in a form of a check at the end of each week during their followup visit.

WITHDRAWAL OF PARTICIPANTS

A participant will be withdrawn from the research without their consent if there is: 1) refusal to follow the medication protocol, and/or 2) refusal to answer study questionnaires, 3) the participant fails to respond to contact attempts from the study team.

RISKS TO PARTICIPANTS

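### The only suicidality check named after the last dose is limited to women with an earlier abnormality, so ideation that first appears after stopping would not be systematically assessed

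*Protocol*

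**What the plan says.** The timing rule is in the protocol under Specific Instrument Use, C-SSRS: "Suicidal ideation will be assessed at baseline, during, and 28 days after treatment cessation if there were any abnormalities during the trial". The condition can only sensibly attach to the third time point, because a baseline assessment cannot depend on what happens later. The word for abnormalities is not defined; presumably it means an abnormal suicidality finding.

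The remaining text on this point is spread across several sections:

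- **Figure 3** (three-week trial) lists the C-SSRS at intake and at the day 7, 14 and 21 visits.
- **Figure 4** lists it every four weeks under continuation treatment. Its delivery column holds only the Peripartum Events Scale and blood samples.
- **Objectives** promises follow-up for women who stop: "After the initial trial, a continuation period or a mirtazapine tapering regimen with monitoring will be offered".
- **Mirtazapine Regimen** gives the taper from 45 mg: "she will begin a taper (by week) of 30 to 15 to 7.5 to 0 mg". It returns a woman to her previous effective dose if she relapses or has discontinuation symptoms, and lets her try the taper again. It also provides for early stopping: "Mirtazapine treatment will continue unless the participant withdraws consent, experiences a limiting side effect", among other reasons.
- **Compensation** implies further contact: "If a participant wishes to participate in the continuation period or a mirtazapine tapering regimen, they will continue for 5 additional weeks".
- **SAP, Aim 3** assesses the taper through somatic symptoms on the Asberg Side Effects scale.
- **Trial Stopping Criteria** makes new-onset suicidal thoughts or behaviours a reason for an individual woman to leave the trial.

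**The concern.** A check that depends on an earlier abnormality re-examines women who have already been identified. It cannot find a first occurrence after withdrawal.

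The documents themselves give reasons to look at that period. Mirtazapine is marketed as an antidepressant. The Background says that people with unremitting symptoms often have secondary depressive and anxiety symptoms. The taper text foresees relapse and discontinuation symptoms. The individual stopping rule for new-onset suicidal thoughts accepts that these can arise in women who passed screening.

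What is at stake is the safety of individual women and the completeness of the safety record that a later randomised trial would inherit. The estimates in the SAP are not at stake.

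**Working it through.** There is no stated figure to reproduce. The check is to follow a woman through each route off the drug and ask whether any text names a suicidality assessment after her last non-zero dose. Suppose throughout that she has had no abnormality.

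1. **She tapers straight after the three-week trial.** Figure 3 ends with the day-21 C-SSRS, when she is still on drug. Neither figure is a data-collection table for the taper. SAP Aim 3 names only the Asberg scale. The 28-day check does not apply, because its condition is not met. C-SSRS named after the last dose: 0.

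2. **She continues, then tapers later.** Figure 4 gives the C-SSRS every four weeks while she is on maintenance. Its title and the accompanying text tie it to women who continue treatment. Once she stops, it no longer clearly applies. C-SSRS named after the last dose: 0.

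3. **She is treated until delivery and stops then.** The delivery column of Figure 4 contains no C-SSRS. C-SSRS named after the last dose: 0.

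4. **She stops before day 21**, for example for a limiting side effect or under an individual stopping rule such as the liver or sodium thresholds. The post-trial follow-up text is written for women who go on to continuation or taper, so it does not clearly cover her. Trial Stopping Criteria does not say whether the 28-day check survives an individual stop. C-SSRS named after the last dose: 0.

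The PHQ-9 sits beside the C-SSRS in both figures and on the same days, so it does not fill the gap.

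The taper weeks are a separate question. Cessation is the step to 0 mg, so the reduced-dose weeks can be read as falling *during* treatment in the C-SSRS rule. Against that reading, the taper is placed after the three-week trial and is given to women who choose to stop, with no visit table. The text does not settle it. The ambiguity does not affect the result above, which concerns the time after the last non-zero dose.

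The number of women affected cannot be derived. Planned enrolment is 25, which is the ceiling. The SAP's sample-size section reports 2 enrolled at Northwestern before the study closed. The documents give no rate of suicidality after withdrawal.

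**The case against.** The strongest case for leaving the text alone is that conditional follow-up is a reasonable choice in a screened group. Figure 6 excludes "Subjects with active depression, or history of or current active suicidal ideation or attempt", and four C-SSRS fall within the first 21 days. The 28-day point was chosen as follow-up of an observed abnormality, not as general screening. Other safeguards exist: the DSMB reviews whether the taper controls discontinuation symptoms, relapse leads to re-dosing, the Asberg scale includes a summary of overall distress, and adverse events are tracked. All of this stands and keeps the severity low. None of it is a suicidality assessment, so it narrows the gap without closing it.

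A reader might infer three stronger things that the documents do not support.

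- **That women who stop lose contact with the team.** They do not: monitoring is offered, and the Compensation section speaks of a weekly payment ("Compensation will be provided in a form of a check at the end of each week during their followup visit"). For women who enter very early in pregnancy it adds that "they will have monthly visits after the 8 weeks is completed". Those monthly visits might follow the Figure 4 set, which includes the C-SSRS, although the text does not say so for women off drug.
- **That a known number of taper and off-drug visits lack the C-SSRS.** Any such count rests on a payment paragraph that names no instrument for any visit, including the three trial weeks. Its weekly pattern also sits awkwardly with the monthly follow-up of continuing women in Mirtazapine Regimen. Exact visit days would be assumptions.
- **That the taper weeks are definitely uncovered.** As shown in the working, that is unclear.

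Visit-level detail may also sit in the manual of operating procedures, which is not available here. A manual could add assessments, but the protocol's rule as written makes the post-cessation one conditional.

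**Conclusion.** The concern holds for the period after the last dose. For a woman without an earlier abnormality the plan names no suicidality assessment once she has stopped, whichever route she takes, so a first occurrence would depend on spontaneous report or on unstructured contact. For the taper weeks the finding is only that coverage is unclear.

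This is a low-severity safety improvement. It rests on reading the condition as applying to the 28-day point alone, and on the absence of any other named instrument in the two documents. It does not claim that the event is likely, and it changes no aim, endpoint or analysis. With only 2 women enrolled before closure, its practical value lies mainly in the later definitive trial, which the protocol says will be built from this study's operating manual.

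**What to change.** Make three wording changes in the protocol.

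1. In the C-SSRS entry, delete the condition. Every woman who stops, including early stoppers and those who taper after maintenance, then has a C-SSRS 28 days after the last non-zero dose of her final taper. Give it at a visit if one is due, and otherwise by telephone or telehealth, the route already used for the day-2 side-effect call.
2. State that assessment during treatment includes every taper week, whenever the taper takes place. Tying this to the taper itself, and not to the weeks straight after day 21, also covers women who taper after maintenance.
3. In Trial Stopping Criteria, state that an individual stop does not cancel the 28-day check.

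The schedule figures should carry the same entries.

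The cost is one short extra contact for each woman who stops and has no visit due at that point, which is at most 25 women at planned enrolment, plus a short questionnaire at taper contacts. Repeat tapers add to both, so neither is a fixed number per woman. Existing staff can do the work. Sample size and analysis are unaffected.

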Med Log \rightarrow	\rightarrow	\rightarrow	\rightarrow	\rightarrow	\rightarrow	\rightarrow	\rightarrow	\rightarrow	\rightarrow	\rightarrow	\rightarrow	\rightarrow	\rightarrow	\rightarrow	\rightarrow	\rightarrow	\rightarrow	\rightarrow	\rightarrow	\rightarrow		

Trial Protocol Overview (Figure 3).

Acceptability. The participant's medical status and drug treatment for sNVP will be reviewed by the study obstetrician. As in clinical practice, other anti-emetic drugs may be continued if desired by the participant and recommended by the obstetrician. The subject's decision to accept or decline will be recorded and she will be asked to provide the reason(s) for her decision. Pregnant persons who enroll will be given mirtazapine to begin treatment that evening or at a time recommended by the obstetrician. Intervention for pregnant persons who decline to participate will be coordinated by their obstetrical care professional.

Mirtazapine Regimen. The dose of mirtazapine for depression (15-45 mg/day) may not be the same as for achieving its antiemetic effect because the targeted receptors differ. We will begin with 15 mg, which is the lowest dose of the oral disintegrating tablet available. A telephone or telehealth follow-up for side effects will be conducted on day 2. Dose increases will occur weekly during the visits as depicted in Figure 3 unless the patient has prohibitive side effects or remission of sNVP. Remission is defined as a PUQE score of 3 (no symptoms) or 4 (1 hour or less of nausea without retching or vomiting). Side effects assessment will occur the day after each dose increase to evaluate tolerability. Reduction to the previous dose will occur if side effects are burdensome. Although the modal dose of mirtazapine from case reports is 30 mg. tolerability studies in persons with NVP have not been published. Steady-state plasma concentrations of mirtazapine occur within 5 days³² and will be achieved across the week prior to dose escalations. Weekly plasma concentrations will be obtained to confirm absorption of mirtazapine and explore associations with side effects. Sampling will occur at a consistent time of day for each woman; ideally, the time will be in the late afternoon during the drug elimination phase as close to the trough concentration as feasible. Adverse events will be reviewed by the DSMB after every 5 subjects to determine whether a protocol or dosing change is warranted.

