Side Effect Assessment, Before mirtazapine treatment, a comprehensive metabolic profile and urinalysis will be obtained as standard of care. An ECG also will be performed. The degree of QT prolongation observed with both 45 mg (therapeutic) and 75 mg (supra-therapeutic) doses of mirtazapine was not clinically meaningful,⁴⁷ and QTc ≥500 msec was not observed among mirtazapine-treated patients.⁵⁰ The drug regimen to which mirtazapine may be added will be reviewed by [name], a fellowship-trained clinical pharmacologist and obstetrician, for QTc prolongation risk prior to mirtazapine administration, or [name], an attending obstetriciangynecologist in Obstetrical Triage, or [name], the PI, a perinatal psychopharmacologist. Side effects will be assessed with the 14-item Asberg Side Effects (ASE)⁵¹ scale, which was adapted by our team for SSRI-treated pregnant persons.^{52,53} The ASE guantifies discomforts from mild to severe and a summary of overall distress. Serotonin hyper-stimulation will be reviewed with Hunter's Decision Rules for Diagnosis of Serotonin Toxicity (SS).⁵⁴ SS is characterized by tachycardia, diaphoresis, myoclonus and tremor.⁵⁵ The incidence of SS is infrequent (9/10,000) as shown in a retrospective cohort study⁵⁶; however, ondansetron, metoclopramide and mirtazapine have been associated with SS during monotherapy and with other serotonergic drugs⁵⁷, although rarely in young persons.⁵⁸ Treatment includes drug discontinuation, benzodiazepines and the anti-serotonergic drug cyproheptadine.

Specific Instrument Use

Pregnancy Unique Quality of Emesis (PUQE)⁴³ **scale (Figure 2):** We will utilize the PUQE scale to capture the severity of nausea and vomiting in pregnancy based on three physical symptoms: nausea, vomiting, and retching over the previous 24 hours. A PUQE score of < 6 is considered mild, a score from 7-12 is moderate, and a score of 13+ is considered severe. This scale will be entered daily in REDCap directly by the participant.

Self-Administered Comorbidity Questionnaire (SCQ)⁵⁹**:** The Comorbidity Questionnaire (CQ) assesses comorbid conditions in clinical and health services research. The questionnaire is self-administered, short, easily understood, and can be completed by individuals without any medical background. It also allows the subject to note the severity of each comorbid conditions and their perception of its impact on their function.

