Subject plasma and blood for DNA extraction will be stored in a -70°C freezer in the Northwestern Core Laboratory. All samples will be de-identified and labeled with the Northwestern Medicine clinical research unit ID, the subject ID, the date of collection, the type of sample collected (e.g. plasma), and the corresponding timepoint. Samples will not contain protected health information or any other type of identifiable information. Mirtazapine Assay. [name], Scientific Advisor of the Clinical Pharmacology Core, will analyze plasma for concentrations of mirtazapine and desmethylmirtazapine by high-performance liquid chromatography-tandem mass spectrometry after sample preparation by solid-phase extraction (see letter of support).^{64 65} the lower limit of quantitation will be 0.5 ng/mL. The linear range of the calibration curve will be 0.5--250 ng/mL. Accuracy will be within ±10% and precision 10% or less. [name] will model the serial concentration data for analyses to determine associations with variables (tolerability, side effects, pharmacogenetic data, adverse events) and whether remission is associated with mirtazapine concentration, with statistician [name], MS, and our team.

We will seek consent from our subjects to have their fully de-identified data and biospecimens included in the NICHD Data and Specimen Hub (DASH-https://dash.nichd.nih.gov/) for future studies.

SHARING RESULTS WITH PARTICIPANTS

No research data will be shared with participants. Because this is an open trial of a marketed drug, the participants will have direct knowledge of clinical information that may be useful in the

future, such as their response to mirtazapine, the efficacious dose, and the duration of treatment required.

STUDY TIMELINES

It will take approximately 18 months to enroll all study participants (Figure 5). We will evaluate subject flow and safety analyses in weekly research meetings, which will be conducted throughout the project.

Figure 5. Project Time Line						
Year	Study Months	Study Tasks	Cum. Enroll			
Pre- Award	10/21- 02/22	Submit IRB and IND applications, finalize manual of operations, develop recruitment tools, inform obstetrical practices of upcoming E-SNAP study startup	0			
02/22	01-03	Finalize and test REDCap database; open recruitment	0			
04-1	04-12	Enroll 1-2 new subjects/month; DSMB review after every 5 subjects are enrolled	15			
02/23-	13-18	Enroll 1-2 new subjects/month; DSMB review after every 5 subjects are enrolled	10			

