We will evaluate the potential need for change in the dosing for the subsequent RCT by balancing the time to response against the emergence of any side effects. For example, if the 15 mg/day dose is well tolerated but the major symptom reduction occurs at 30 mg/day, we will consider the advisability of a more assertive dosing regimen with our DSMB and FDA consultants.

Aim 3. The drug tapering strategy will be assessed by evaluating the emergence of somatic symptoms on the Asberg side effects profile during the taper. Obtaining weekly plasma concentrations in the initial 21-day trial allows an exploration of whether a relationship between mirtazapine concentration and antinauseant/ antiemetic efficacy is likely in this group of women. The patient's genotypes and corresponding phenotypes (ultrarapid, rapid, intermediate, poor metabolizers--by specific enzyme) will be evaluated for their relationship to plasma mirtazapine concentrations. Biotransformation is mediated by CYP2D6, CYP3A4, and 1A2.²

Aim 4. Evaluate the maternal and fetal safety of mirtazapine. The maternal and neonatal outcomes from the PES will be reviewed for consistently reported events across subjects. We will compare the mirtazapine exposure data to that of women who have taken SSRI through pregnancy in our Obstetric-Fetal Pharmacology U54 study (N=88), Optimizing Medication Management for Mothers with Depression. Neonatologist [name] (see letter of support) will collaborate with our team to interpret the OPTI-MOM neonatal outcome data from the PES in the proposed trial (fetal exposure to mirtazapine) and compare it with the PES from our current OPTI-MOM subjects (fetal exposure to SSRI antidepressants). We have used these measures in our studies of SSRI exposure on neonates.³ The PES includes medical and obstetric risk factors, time in the delivery/ operating room, fetal monitoring, surgical complications, infant anthropometrics, special care/NICU admission, and post-birth complications. We will compare data using t-tests, chi-square test, and nonparametric tests as appropriate according to the type of data and their distributions.

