Sample Size Considerations. The proposed study is not powered nor expected to evaluate the efficacy of mirtazapine for sNVP. To estimate a preliminary sample size for the efficacy of mirtazapine for NVP/HEG for the initial 3 week trial, we will assume 80% power, two-sided significance=.05, and a standard deviation of 2.1 (derived from Koren et al⁴), and a moderately severe PUQE score (\approx 10) at study entry. The standard deviation of the change in PUQE scores from baseline to week 3 is conservatively estimated to be 2.97 by assuming that the correlation is zero. With 20 subjects, we can detect a 23% reduction in mean symptom scores (a 2.3 point decrease in PUQE scores). Based on the case studies, we anticipate a more favorable symptom reduction than 2.3 points. To allow a 20%

dropout rate, we will enroll 25 subjects. We enrolled 2 participants, who completed the 3- week study at Northwestern, before the study was closed.

References.

- 1. Trials CTRo. The CONSORT Flow Diagram. Accessed.

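### The exploratory concentration-efficacy analysis names remission (PUQE 3 or 4) in the protocol and only efficacy in the SAP; it should use the full PUQE score, which is already collected at every plasma visit.

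*Protocol*

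**What the plan says.** The only place that names an efficacy variable for the concentration analysis is the Mirtazapine Assay paragraph under Data and Specimen Banking in the protocol. There the serial concentrations are to be modelled to see, among other things, "whether remission is associated with mirtazapine concentration". Under Mirtazapine Regimen the protocol states: "Remission is defined as a PUQE score of 3 (no symptoms) or 4 (1 hour or less of nausea without retching or vomiting".

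SAP Aim 3 puts the question more broadly, as "an exploration of whether a relationship between mirtazapine concentration and antinauseant/ antiemetic efficacy is likely in this group of women". It gives no outcome variable and no model. The protocol's fifth aim (Objectives) does not mention efficacy here: "Explore the relationship of study drug dose and plasma concentration with side effects and pharmacogenetics by obtaining weekly plasma".

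Protocol Figure 3 schedules PUQE and plasma together on days 7, 14 and 21. Of PUQE, Specific Instrument Use says: "This scale will be entered daily in REDCap directly by the participant". Study Endpoints makes change in PUQE the primary outcome. The SAP analyses remission only in Aim 2, as time to remission, with Kaplan-Meier curves and Cox models.

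**The concern.** PUQE is the sum of three items scored 1 to 5, so it has 13 levels. Remission keeps only whether the score is in the bottom two. Women enter at 10 to 15, so a woman who falls from 14 to 5 counts the same as one who does not improve. With about 20 evaluable women, such a cut can leave very few on one side. The paired full score already exists at each plasma visit, and the documents give no reason for preferring the cut in this analysis.

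What is at stake is the quality of the information handed to the phase 3 design. A real relation between concentration and symptom relief would be estimated less precisely and seen less often than the same data allow.

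**Working it through.** **Inputs.** From SAP Sample Size Considerations: entry PUQE about 10, SD 2.1, SD of change 2.97, 20 evaluable women, 80% power, two-sided 0.05, and "a 2.3 point decrease in PUQE scores" as the detectable difference. From the protocol: remission is PUQE of 4 or less. The correlation between concentration and PUQE is not in the documents. I assume 0.5 and show 0.4 to 0.6.

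**The plan's own figures.**
- SD of change with zero correlation: 2.1 × √2 = 2.97. This agrees.
- Enrolment: 20 / 0.8 = 25. This agrees.
- Detectable difference at 80% power: (1.960 + 0.842) × 2.97 / √20 = 1.86 (normal), or 1.96 with a t-test. The stated 2.3 does not reproduce. At 2.3 points the power is 93% (normal) or 91% (t). I use 2.3 below only as the plan's stated value.

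**Expected remitters at day 21.** Mean = 10 − 2.3 = 7.7. Count = 20 × Φ((c − 7.7) / SD), with c = 4, or 4.5 after continuity correction.
- SD 2.1: Φ(−1.76) = 0.039 gives 0.8; Φ(−1.52) = 0.064 gives 1.3.
- SD 2.97 (the SD of change, which applies if all women enter near 10): Φ(−1.25) = 0.106 gives 2.1; Φ(−1.08) = 0.141 gives 2.8.

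That is about 1 to 3 of 20. With SD 2.1 the chance of no remitter at all is (1 − 0.064)^20, about 27%. The count depends strongly on the fall: 3.4 to 6.1 at 4 points, 6.3 to 8.7 at 5 points, and 10 to 12 at 6 points.

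**Single-visit power.** Simulation with n = 20 and correlation 0.5. PUQE is rounded and held within 3 to 15. The score is tested by Spearman correlation and remission by an exact Mann-Whitney comparison of concentration. Trials without both groups count as non-significant.

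| Mean PUQE | SD | Full score | Remission |
|---|---|---|---|
| 7.7 | 2.1 | 57% | 9–10% |
| 7.7 | 2.97 | 58% | 22–23% |
| 6 | 2.1 | 57% | 32% |
| 6 | 2.97 | 56% | 35% |
| 5 | 2.1 | 57% | 40% |
| 5 | 2.97 | 55% | 39% |

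Repeat runs at means 6 and 5 put the remission figures within about 30–42%. A t-test in place of the rank test raises them somewhat: to 16% and 27% at mean 7.7, and to at most about 44% at mean 5. Over correlations of 0.4 to 0.6, the smallest gap was 36% against 26% and the largest 77% against 14%.

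**Repeated measures.** With an assumed within-woman residual correlation of 0.5 to 0.8, and again a correlation of 0.5, PUQE over the three visits had about 67–79% power. Remission across visits had 13–57%, and time to remission 24–68%. The score had more power in every scenario compared.

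These figures compare outcome scales. They do not model dose rising by week or being held at remission, so they are not the power of the adjusted model proposed below.

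**The case against.** The strongest reply is that the documents never commit to a yes/no test. The assay paragraph names no model, SAP Aim 3 is broad enough to cover the full score, and the only remission analysis that the SAP specifies is time to remission on daily scores. This stands in part. A reader might infer that the SAP imposes the cut, but it does not: the protocol names remission and the SAP leaves the scale open. Time to remission also uses more data, since more women remit on some day than are in remission on day 21. It narrows the gap but does not close it.

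A reader might also infer that the cut loses most of the power at the plan's target. The documents do not support that. The 2.3 points is a detectable difference, and the SAP says a larger reduction is anticipated. A loss of more than half is confined to falls near 2.3 points with remission taken at a single visit.

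A third tempting inference is that a null result would lead the sponsor to drop concentration- or genotype-guided dosing. No decision rule in the plan says so. SAP Aim 2 bases later dosing on time to response weighed against side effects, and SAP Aim 3 relates genotype to concentration, not to remission.

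It is also fair that the plan calls this work exploratory and unpowered, and that the SAP reports only 2 women enrolled before closure, so neither analysis can be estimated in the actual data. The point therefore concerns the plan as written and any later trial built from it. Being exploratory is no reason to discard information already collected.

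**Conclusion.** The point holds as a minor improvement. Protocol and SAP describe the efficacy side of the concentration analysis differently, neither fixes a model, and the one variable named is a cut near the floor of a score available in full at the same visits.

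The single-visit loss is large if the mean fall is only about 2.3 points: 57% against about 10% or 23%. It is smaller but still material at falls of 4 to 5 points: about 55–57% against 30–42% by rank test. Against time to remission the comparison is 67–79% for the three-visit score and 24–68% for remission.

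These sizes rest on an assumed correlation of 0.5, roughly normal scores, 20 evaluable women and, for repeated visits, an assumed within-woman correlation of 0.5 to 0.8. The direction was the same in every scenario examined.

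**What to change.** In the protocol's Mirtazapine Assay paragraph and in SAP Aim 3, name the PUQE score at days 7, 14 and 21 as the main efficacy variable for the exploratory concentration analysis. Fit a mixed model of PUQE on log mirtazapine concentration at the same visit, with baseline PUQE and week as covariates and a random intercept per woman. Report the slope with its 95% confidence interval. Keep remission against concentration as a supportive or descriptive display.

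Add one caution. Under Mirtazapine Regimen the dose is not escalated once a woman is in remission, so response feeds back on concentration whichever scale is used. The slope should not be read as causal.

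The cost is a few sentences in the two documents and no new data. The downside is that a slope in PUQE points is slightly less direct to read than remission.
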